### 5.3.5 Other safety parameters

#### 5.3.5.1 Pulmonary Function Testing

Spirometry measurements will be performed on the device of the investigational sites. The spirometer and its use must meet American Thoracic Society (ATS) / European Respiratory Society (ERS) criteria [\[P05-12782\]](#) (this includes daily calibration, daily calibration checks and weekly linearity checks before performance of the measurements). In addition peak flow must be reached earlier than 120 ms after the extrapolated start of the maneuver in order to fulfil the acceptable criteria for a forced spirometry maneuver.

### 5.3.6 Assessment of adverse events

#### 5.3.6.1 Definitions of AEs

##### **Adverse event**

AE is defined as any untoward medical occurrence in a patient or clinical investigation subject administered a medical product and which does not necessarily have to have a causal relationship with this treatment.

An AE can therefore be any unfavorable and unintended sign (including an abnormal laboratory finding), symptom, or disease temporally associated with the use of a medicinal product, whether or not considered related to the medicinal product.

##### **Serious adverse event**

A serious adverse event (SAE) is defined as any AE which:

- results in death,
- is life-threatening,
- requires in subject hospitalization or prolongation of existing hospitalization,
- results in persistent or significant disability or incapacity,
- is a congenital anomaly/birth defect,
- or
- is to be deemed serious for any other reason if it is an important medical event when based upon appropriate medical judgment which may jeopardize the subject and may require medical or surgical intervention to prevent one of the other outcomes listed in the above definitions.

Life-threatening in this context refers to an event in which the subject was at risk of death at the time of the event; it does not refer to an event that hypothetically might have caused death if more severe.

Every new occurrence of cancer must be reported as a serious event regardless of the duration between discontinuation of the drug and the occurrence of the cancer.

##### **AEs considered “Always Serious”**

In accordance with the European Medicines Agency initiative on Important Medical Events, Boehringer Ingelheim has set up a list of AEs, which by their nature, can always be considered to be “serious” even though they may not have met the criteria of an SAE as given above.

The latest list of “Always Serious AEs” can be found in the Remote Data Capture (RDC) system. These events should always be reported as SAEs as described in [Section 5.3.7](#).

##### **Adverse events of special interest (AESIs)**

The term AESI relates to any specific AE that has been identified at the project level as being of particular concern for prospective safety monitoring and safety assessment within this trial, e.g. the potential for AEs based on knowledge from other compounds in the same class. AESI

need to be reported to the Sponsor's Pharmacovigilance Department within the same timeframe that applies to SAE, see [Section 5.3.7](#).

The following are considered as AESIs:

#### Hepatic injury

A hepatic injury is defined by the following alterations of hepatic laboratory parameters:

- an elevation of AST and/or ALT  $\geq 3$  fold upper limit normal (ULN) combined with an elevation of total bilirubin  $\geq 2$  fold ULN measured in the same blood draw sample, and/or
- marked peak aminotransferase (ALT and/or AST) elevations  $\geq 10$  fold ULN

These lab findings constitute a hepatic injury alert and the subjects showing these lab abnormalities need to be followed according to the "DILI checklist" provided via the RDC system.

In case clinical symptoms of hepatic injury (for example, icterus, unexplained encephalopathy, unexplained coagulopathy, right upper quadrant abdominal pain) without available lab results (ALT, AST, total bilirubin), the investigator should make sure these parameters are analyzed, if necessary in an unscheduled blood test. Should the results meet the criteria of hepatic injury, the procedures described in the DILI checklist should be followed.

#### Intensity of AEs

The intensity of the AE should be judged based on the following:

- Mild: Awareness of sign(s) or symptom(s) that is/are easily tolerated  
Moderate: Enough discomfort to cause interference with usual activity  
Severe: Incapacitating or causing inability to work or to perform usual activities

#### Causal relationship of AEs

Medical judgment should be used to determine the relationship between an AE and trial medication, considering all relevant factors, including pattern of reaction, temporal relationship, de-challenge or re-challenge, confounding factors such as concomitant medication, concomitant diseases and relevant history.

Yes: There is a reasonable causal relationship between the investigational product administered and the AE.

No: There is no reasonable causal relationship between the investigational product administered and the AE.

[figure not shown]
The reason for the decision on causal relationship for unlisted AEs could be provided in the (e)CRF as deemed necessary by the investigator.

### **5.3.7 Adverse event collection and reporting**

#### **AE Collection**

The following must be collected and documented on the appropriate eCRF by the Investigator:

- From signing the informed consent onwards through the Residual Effect Period (REP), until individual subject's end of trial:
  - All AEs (serious and non-serious), and all AESIs.
- After the individual subject's end of trial:
  - The investigator does not need to actively monitor the subject for AEs but should only report relevant SAEs and relevant AESIs of which the investigator may become aware of.

All AEs which considered as on

treatment please see [Section 7.3.4](#). Events which occurred after the REP will be considered as post treatment events.

### AE reporting to sponsor and timelines

The Investigator must report SAEs, AESIs, and non-serious AEs which are relevant for the reported SAE or AESI, on the BI SAE form via fax immediately (within 24 hours ) to the Sponsor's unique entry point (country specific contact details will be provided in the ISF). The same timeline applies if follow-up information becomes available. In specific occasions the Investigator could inform the Sponsor upfront via telephone. This does not replace the requirement to complete and fax the BI SAE form.

With receipt of any further information to these events, a follow-up SAE form has to be provided. For follow-up information the same rules and timeline apply as for initial information.

### Information required

For each AE, the Investigator should provide the information requested on the appropriate eCRF pages and the BI SAE form, e.g. onset, end date, intensity, treatment required, outcome, seriousness, and action taken with the investigational drug(s). The Investigator should determine the causal relationship to the trial medication and any possible interactions between the investigational drug and a Non-Investigational Medicinal Product (NIMP)/Auxiliary Medicinal Product (AMP) as comment.

The following should also be recorded as an (S)AE in the eCRF and SAE form (if applicable):

- Worsening of the underlying disease or of other pre-existing conditions
- Changes in vital signs, ECG, physical examination and laboratory test results, if they are judged clinically relevant by the Investigator.

If such abnormalities already pre-exist prior trial inclusion they will be considered as baseline conditions.

All (S)AEs, including those persisting after individual subject's end of trial must be followed up until they have resolved, have been sufficiently characterized, or no further information can be obtained.

#### **Screening failures:**

[figure not shown]
SAEs occurring in patients after having discontinued in the trial due to screening failures, i.e. after the screening period and who did not receive any trial medication, are to be reported if the investigator considered the SAE related to the screening procedure. SAEs which occurred during the screening period are to be reported according to standard procedures.

[figure not shown]
#### **Pregnancy:**

In rare cases pregnancy may occur in a clinical trial. Once a subject has been enrolled into this clinical trial and has taken trial medication, the Investigator must report immediately (within 24 hours) a potential drug exposure during pregnancy (DEDP) to the sponsor's unique entry point (country-specific contact details will be provided in the ISF). The Pregnancy Monitoring Form for Clinical Trials (Part A) should be used. The outcome of the pregnancy associated with the drug exposure during pregnancy must be followed up and reported to the sponsor's unique entry point on the Pregnancy Monitoring Form for Clinical Trials (Part B). The ISF will contain the Pregnancy Monitoring Form for Clinical Trials (Part A and B). As pregnancy itself is not to be reported as an AE, in the absence of an accompanying SAE and/or AESI, only the Pregnancy Monitoring Form for Clinical Trials and not the SAE form is to be completed. If there is an SAE and/or AESI associated with the pregnancy an SAE form must be completed in addition.

#### **Exemptions to SAE Reporting**

Not applicable.

[figure not shown]

BAL sample will be taken at time points indicated in the Flow Chart. Instruction describing the BAL procedure is provided in the ISF.

The provided BAL samples will be processed in order to the procedure for BAL and processing provided in the ISF. BAL samples need to be processed directly (within 2 hours maximum) after the sample has been taken.

Cellular fraction will be used for total and differential cell count ([see section 5.1](#)). If sufficient material is available, transcriptome analysis may be performed.

## 5.7 APPROPRIATENESS OF MEASUREMENTS

Measurements performed during this trial are standard measurements and will be performed  to monitor safety aspects in an appropriate way.

The PK parameters and measurements outlined in [Section 7.3.5](#) are generally used as measurements to assess drug exposure.

The scheduled measurements are appropriate to see drug induced changes in vital signs, lung function, standard laboratory values and ECG.

These primary and secondary endpoints are standard and accepted for evaluation of pharmacodynamic parameters of an oral drug, and they are widely used in this kind of studies.

Therefore, the appropriateness of all measurements applied in this trial is given.

## 6. INVESTIGATIONAL PLAN

### 6.1 VISIT SCHEDULE

#### 6.1.1 Adherence to the protocol visits and procedures

Subjects should make all efforts to complete the study which includes the follow-up period and end of trial visit. Investigators should encourage treatment compliance and adherence to the protocol procedures. All subjects are to adhere to the visit schedule as specified in the [Flow Chart](#). All deviations from the planned visit schedule should be documented.

Regarding randomization please refer to [Section 7.6](#).

Regarding removal of subjects please refer to [Section 3.3.4](#).

#### 6.1.2 Visit scheduling

All observations and procedures as mentioned in the [Flow Chart](#) for an individual visit should be performed on the same day. Clinical and safety laboratory evaluation of Visit 1 can be repeated maximum twice within the screening period for clinical and/or technical reasons (e.g. the blood sample is clotted) based on investigator's judgment. If more than 2 repeated evaluations are necessary the subject will be discontinued from the study and will be marked as screening failure.

At clinic visits, the administration is under the supervision of the investigator or qualified site staff.

All subjects are to adhere to the visit schedule as specified in the [Flow Chart](#). Some flexibility is allowed in scheduling the visits according to visit time windows as specified in the Flow Charts ( $\pm 2$  days during the treatment period for Visits 3, 4, 5 and 6). Visit 7 must be performed on the day following Visit 6.

If any visit has to be rescheduled, subsequent visits should follow the original visit date schedule (calculated from Visit 2). The total treatment period of  $28 \pm 2$  days must not be exceeded, i.e. Visit 6 must be performed between Day 26 and 30 following randomization (Visit 2).

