### 3. DESCRIPTION OF DESIGN AND TRIAL POPULATION

#### 3.1 OVERALL TRIAL DESIGN AND PLAN

An overview of the trial design is shown in Figure 3.1.1.

[figure not shown]

Figure 3.1.1: Study Design

This is a randomized, double-blind, placebo-controlled, parallel-group, single center study to assess the proof of mechanism and safety of BI 1026706 compared to placebo. The respective treatment will be administered orally as tablet twice daily during the 4 week treatment period. The random allocation to active or placebo treatment will have a ratio of 1:1.

A total of 50 subjects will participate in the trial consisting of 2 treatment groups of 25 subjects, each treated for 28 ± 2 days.

This trial consists of 8 Visits. Visit 1 is the screening visit. Between Visits 2-6 subjects will receive either BI 1026706 or placebo for 28 ± 2 days, depending on the treatment group they have been randomized to. In addition, at Visit 6 baseline BAL will be conducted following LPS and saline challenge. At Visit 7 the BAL will be examined for the 24 hours post LPS and saline challenge. Visit 8 is the end-of-trial examination.

The screening period lasts from the signature of informed consent at Visit 1 until randomization (directly followed by first administration of trial medication) on Day 1 (Visit 2).

The screening visit (Visit 1) will take place 3 to 28 days prior to randomization.

The treatment period lasts from the first administration of trial medication on Day 1 (Visit 2) until Day 28 ± 2 days (Visit 6).

The follow-up period lasts from Day 29 (Visit 7) until the End of trial (Day 32 to 34, Visit 8).

Please refer to [Section 8.6](#) for the definition of the end of trial.

Subjects are included in the study once they have signed the informed consent and their participation concludes when they have undergone the last planned visit. The end of trial visit (Visit 8) also needs to be completed if the subject withdraws from or is removed from the trial following randomization ([see Section 3.3.3](#))

All trial relevant documentation will be stored by Boehringer Ingelheim in the Trial Master File (TMF). Trial relevant documentation for the study sites will be filed in the Investigator Site File (ISF).

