### 6.2.3 Follow-up Period and End of Trial

[figure not shown]
#### Details on particular observations and procedures at Visit 7 and 8

Observations and procedures will be performed as mentioned in the [Flow Chart](#). Timing of Visit 7 in relation to Visit 6 is described in section [6.2.4](#).

- Complete physical examination will be conducted
- Alcohol screening at Visit 7
- Vital signs measurement
- ECG recording
- Safety dipstick urine test at Visit 8 including a pregnancy testing for female subjects
- Safety blood sampling and processing

- Treatment compliance check will be performed at Visit 7
- Subjects drug diary will be checked at Visits 7
- AE assessment

- Concomitant therapy documentation and recording, diet and lifestyle restrictions

- 
- Bronchoscopy with retrieval of BAL and biopsies will be performed at Visit 7, 24 hours ( $\pm 1$  h) after LPS challenge at Visit 6. In case of female subjects, a negative urine pregnancy testing is required at Visit 6. Pulse oximetry will be done during bronchoscopy. Trial is completed at Visit 8.

Subjects who took the trial medication and discontinue prematurely should undergo the EOT examination (Visit 8) as soon as possible after the last dose of trial drug.

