6. GENERAL ANALYSIS DEFINITIONS

6.1 TREATMENTS

For basic study information on treatments to be administered, assignment of dose groups, and selection of doses, cf. Section 4 of the CTP.

Subjects will be treated with either

- 100 mg BI 1026706 (test treatment, T) or
- placebo (reference treatment, R),

twice daily for 28 +/- 2 days.

The following separate study analysis phases will be defined for the analyses of AEs, laboratory tests, vital signs and body weight:

- **Screening** (ranging from 0:00 h on day of informed consent until first administration of study drug)
- **On treatment** (separately for each treatment, ranging from the time of first study drug administration [REDACTED] 4 days after the last administration of study drug; note that 4 days after the last trial medication application are defined in CTP Section 5.3.7 as the residual effect period [REP])
- **Post-treatment** (separately for each treatment, ranging [REDACTED] days after the last administration of study drug, i.e. the end of the REP, to start of post-study phase)
- **Post-study** ([REDACTED] after the last administration of study drug or at 0:00 h on the day after the EOT visit, whichever is later)

Note that the post-treatment phase might not exist for individual subjects, e.g. if the EOT visit is [REDACTED] of the last administration of study drug.

Table 6.1: 1 Flow chart of study analysis phases for adverse events, laboratory tests, vital signs and body weight

Study analysis phase	Start	End
Screening	Date of informed consent	Date/time of first administration of study drug
On treatment	Date/time of first administration of study drug	Date/time of last administration of study drug + REP, [REDACTED] * 24 h
Post-treatment ¹	Date/time of last administration of study drug + REP ([REDACTED] * 24 h)	12:00 AM on day after trial completion date
Post study	Date/time of last administration of study drug + REP ([REDACTED] * 24 h) or 12:00 AM on day after trial completion date (whichever is later)	Not defined – a placeholder date is used, e.g. a date after database lock

¹ does not necessarily exist

Displays of AEs, laboratory tests, vital signs and body weight will be presented separately for the treatments, labelled "**BI 1026706**" and "**Placebo**".

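### Visit 8 is counted from Visit 2, not from the last dose, so it can fall before the 4-day residual effect period ends and leave part of the TEAE window without active AE collection

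*Protocol*

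**What the plan says.** **Visit timing.** Protocol Section 6.1.2 states that "Visit 6 must be performed between Day 26 and 30 following randomization (Visit 2"). The same section ties Visit 7 to the day after Visit 6. For everything else the rule is "If any visit has to be rescheduled, subsequent visits should follow the original visit date schedule (calculated from Visit 2"). Section 3.1 gives the position of the last visit: "The follow-up period lasts from Day 29 (Visit 7) until the End of trial (Day 32 to 34, Visit 8"). The flow chart shows the same days. Neither place gives an offset from the last dose.

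**Last dose.** Section 4.1 puts the last dose at home on the evening of Day 28, which is the nominal Visit 6 day. Section 4.1.4.5 allows 19:00 to 22:00, and the dosing flow chart asks for a time close to 22:00 on that day.

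**AE window and AE collection.** SAP Section 6.1 says that "4 days after the last trial medication application are defined in CTP Section 5.3.7 as the residual effect period [REP"]. Protocol Section 7.3.4 counts AEs as treatment-emergent up to the end of that period. Section 5.3.7 has AEs collected from consent "onwards through the Residual Effect Period (REP), until individual subject's end of trial". After that point, "The investigator does not need to actively monitor the subject for AEs but should only report relevant SAEs and relevant AESIs" that come to notice. Section 6.2.3 adds "Trial is completed at Visit 8".

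**Early discontinuers.** Under Section 6.2.3 they "should undergo the EOT examination (Visit 8) as soon as possible after the last dose of trial drug".

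**The concern.** The counting window for TEAEs moves with the last dose. The last scheduled AE assessment does not: it stays on the Visit 2 calendar. When Visit 6 is late, Visit 8 can come first. The two limits in Section 5.3.7 (through the REP, and until end of trial) then disagree, and the visible text schedules no later contact.

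The number of subjects with TEAEs is a listed safety endpoint (Section 5.1). A new non-serious AE that starts between Visit 8 and the end of the REP belongs in that count but may never be recorded. The SAP phase rules would place such an event correctly if it were in the database; they cannot collect it.

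The late-Visit-6 subjects are also the ones seen soonest after the second bronchoscopy. With Visit 6 on Day 30, that bronchoscopy is on Day 31 and Visit 8 can follow 1 to 3 days later, against 3 to 5 days on the nominal schedule. Section 2.3.1 names lung infection and fever among the procedure risks, and SAP Section 7.8.1 gives procedural and LPS-related on-treatment AEs their own tables.

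**Working it through.** This is calendar arithmetic; no power or sample-size formula is involved.

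**Inputs**
- Visit 6 day: 26 to 30 (Protocol 6.1.2). This reproduces the stated 28 ± 2 days: 28 − 2 = 26 and 28 + 2 = 30.
- Visit 8 day: 32, 33 or 34 (Protocol 3.1 and flow chart).
- Last dose: 22:00 on the Visit 6 day (dosing flow chart); earliest permitted time 19:00 (4.1.4.5).
- REP: 4 × 24 = 96 h (SAP 6.1).
- Visit 8 clock time: not stated. Assumed 08:00 to 16:00.

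**Formula.** End of REP = Visit 6 day at dose time + 96 h. Gap = max(0, end of REP − Visit 8 time).

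Example: Visit 6 on Day 30 with a 22:00 dose gives a REP ending on Day 34 at 22:00. Visit 8 on Day 32 at 08:00 is 2 days and 14 h earlier, so the gap is 48 + 14 = 62 h. At 16:00 it is 48 + 6 = 54 h.

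**Hours of REP without active AE collection, 22:00 dose**

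| Visit 6 | REP ends (22:00) | Visit 8 Day 32 | Day 33 | Day 34 |
|---|---|---|---|---|
| Day 26 | Day 30 | 0 | 0 | 0 |
| Day 27 | Day 31 | 0 | 0 | 0 |
| Day 28 | Day 32 | 6–14 | 0 | 0 |
| Day 29 | Day 33 | 30–38 | 6–14 | 0 |
| Day 30 | Day 34 | 54–62 | 30–38 | 6–14 |

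Pairs with a gap: 1 + 2 + 3 = 6 of 5 × 3 = 15. The largest gap is 54/96 to 62/96, or 56% to 65% of the REP. After a Day 30 Visit 6, no permitted daytime Visit 8 covers the REP.

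**Sensitivity**
- *Dose at 19:00.* Every gap is 3 h shorter (51–59, 27–35 and 3–11 h for Day 30). The same 6 pairs remain.
- *Collection credited to midnight at the end of the Visit 8 day, 22:00 dose.* Pairs 28/32, 29/33 and 30/34 close. Three remain: 29/32 and 30/33 at 22 h, and 30/32 at 46 h.
- *Visit 6 never later than Day 28,* as the −2 window in the dosing flow chart would imply. Only 28/32 remains, at 6–14 h.

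**Early discontinuers.** If Visit 8 takes place 24, 48 or 72 h after the last dose, 96 − 24 = 72, 96 − 48 = 48 or 96 − 72 = 24 h of the REP is uncovered.

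**The case against.** The strongest reply is that Section 5.3.7 already requires AE collection through the REP, so a site could read it as a duty to keep asking after Visit 8. Part of that section is also redacted: the 4-day definition that the SAP attributes to it is not visible, and there may be further AE-window text. This shows the intent, and it limits any claim about later contacts to the text that can be read. But the same line ends at the subject's end of trial, the next one lifts active monitoring, and no visit follows Visit 8.

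A second reply is that Day 32 to 34 may be only a nominal label, since Section 3.1 also calls Visit 7 Day 29 although Visit 7 moves with Visit 6. Section 6.1.2 also uses the word should. However, that section makes an explicit exception for Visit 7 and none for Visit 8.

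Third, at whole-day resolution the nominal design is aligned, because 28 + 4 = 32. This stands: with an on-time Visit 6 the gap is under a day and depends on the assumed clock time. It does not remove the 22 to 46 h gaps that remain after midnight crediting when Visit 6 is on Day 29 or 30.

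Fourth, the consequence is limited. AEs are assessed at Visit 7, during a stay of about 8 hours, and again at Visit 8. Known AEs are followed up, and relevant SAEs and AESIs are still reported when they come to notice. Nothing in the documents indicates that procedural or LPS-related AEs tend to appear only after Visit 8. All of this stands and is why the point is minor.

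**Conclusion.** The concern holds and is minor. The schedule allows Visit 8 to precede the end of the REP in 6 of 15 permitted day pairs, by up to about 62 of 96 h. It always does so for a daytime Visit 8 after a Day 30 Visit 6. What may be lost is mainly new non-serious AEs in descriptive safety tables. Both arms are affected alike, and the primary endpoint and its analysis are not affected.

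The result rests on the 4-day REP in the SAP, on Visit 8 staying at Day 32 to 34 as Section 6.1.2 directs, and on an assumed Visit 8 between 08:00 and 16:00. The pair count is not a frequency: the documents do not show how often Visit 6 would fall on Day 29 or 30.

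**What to change.** Define Visit 8 from the actual last dose: at least 96 h after it, for example 5 to 7 days after the actual Visit 6. State this in the flow chart and in Sections 3.1 and 6.1.2, and exempt Visit 8 from the rule that counts visits from Visit 2. Check: Visit 6 + 5 days at 08:00 to 16:00 is 106 to 114 h after a 22:00 dose, so the REP is covered for every Visit 6 day.

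For early discontinuers, keep the prompt Visit 8 in Section 6.2.3 and add one AE phone contact at 96 h after the last dose.

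**Cost.** One short amendment; the sponsor decides whether it is administrative. When Visit 6 is on Day 30, Visit 8 moves from Day 32–34 to Day 35–37. After an on-time Visit 6 a Day 32 visit is no longer possible, and the in-person check comes 4 to 6 days after the second bronchoscopy instead of 3 to 5. There is one phone call per early discontinuer. The SAP needs no change.

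If the sponsor prefers to leave Visit 8 where it is, an AE phone contact at the end of the REP for every subject whose Visit 8 came earlier would also close the collection gap. It would not lengthen the short interval between the second bronchoscopy and Visit 8 after a late Visit 6.

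The same amendment could tidy some wording: refer to the day of Visit 6 instead of Day 28 in Sections 4.1 and 4.1.4, align the −2 window in the dosing flow chart with ±2, and add Visit 7 to Section 4.1.4.4. These are clerical and do not bear on the gap.
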